13.1 Adverse Events

An AE is any untoward medical occurrence in a subject or clinical investigation subject administered a pharmaceutical product (which does not necessarily have a causal relationship with this treatment) reported during or after having received the investigational drug/procedure. An AE can therefore be any unfavorable and unintended sign (including an abnormal laboratory finding), symptom, or disease

temporally associated with the use of an investigational product (IP), whether or not related to the IP. Treatment-emergent adverse events (TEAEs) are defined as any event that occurs or worsens on or after the first dose of study medication. All TEAEs will be collected from the first administration of IP until completion of the final visit.

A serious adverse event (SAE) is an AE that results in any of the following outcomes: death, life-threatening, persistent, or significant disability/incapacity, prompts a hospital admission or prolongs hospitalization, congenital anomaly/birth defect, or other important medical events. All SAEs will be collected from the time of informed consent until completion of the final visit.

All AEs will be evaluated by the Investigator/designee for duration, severity, seriousness, and relationship to investigational product. In addition, the actions taken for the AE will also be documented on the eCRF. Only symptoms that increase in severity or frequency after IP administration or new symptoms of illness will be recorded as AEs in the eCRF. If the event reflects worsening symptoms, then this should be captured in the event term. Untoward medical events which occur after signature of the informed consent but before IP administration will be recorded as medical history.

Serious adverse events recorded in the eCRF which began prior to the first dose of study medication will not be included in the summary tables but will be included in the AE data listings. AEs will be coded using MedDRA Version 23.1. Severity of AEs will be assessed as Grade 1 (lowest severity) to 5 (highest severity) using the National Cancer Institute Common Terminology Criteria for Adverse Events (NCI-CTCAE) Version 4.03. Relationship to study drug will be categorized as Not Related, Unlikely, Possible, Probable, and Related. Related AEs will be classified as those categorized as Probable, Possible, Related; or those missing an assessment of relationship to study drug.

An overall summary will be presented that includes the number of TEAEs and the number and percentage of subjects who experienced at least one TEAE by dose group and for all subjects. This summary will also include SAEs, drug-related TEAEs, drug-related SAEs, Grade 2 or higher TEAEs, drug-related Grade 2 or higher TEAEs, TEAEs by maximum CTCAE grade, TEAEs leading to study drug withdrawal, and TEAEs leading to death.

Separate summaries will be provided for TEAEs using discrete summary statistics and presented by dose group and for all subjects by SOC and PT. If a subject reports the same PT multiple times within the same SOC, that PT will only be reported once within that SOC. If a subject reports multiple conditions within the same SOC, that SOC will only be reported once. In the summary, SOC and PTs within each SOC will be listed in order of decreasing frequency for all subjects. The summaries include:

- All TEAEs
- Drug-related TEAEs
- SAEs

A summary of TEAEs will be provided by dose group and for all subjects by PT only. In the summary, PTs will be listed in order of decreasing frequency for all subjects. In addition, summaries of TEAEs by maximum CTCAE grade will be presented using discrete summary statistics by SOC, PT, maximum grade for each dose group and all subjects. AS To count the number of subjects with any TEAEs, if a subject has multiple TEAEs coded to the same SOC, or multiple TEAEs coded to the same PT within the same SOC, the subject will be counted once under the maximum grade.

Individual subject listing will be provided for all AEs, SAEs and AEs leading to study drug withdrawal.

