### 10.1.3 Onset of Adverse Events

The Investigator will classify the onset of each AE relative to the following stages of treatment:

- During AT-1501 infusion
- After AT-1501 infusion

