ICH	International Conference on Harmonisation
IL6	Interleukin 6
IP	Investigational Product
IV	Intravenous
MedDRA	Medical Dictionary for Regulatory Activities
NCI-CTCAE	National Cancer Institute Common Terminology Criteria for Adverse Events

PT	Preferred Term
QTcF	QT Interval Corrected with Fridericia's Formula
RTF	Rich Text Format
SAE	Serious Adverse Event
SAP	Statistical Analysis Plan
SD	Standard Deviation
SDC	Statistics & Data Corporation
SDTM	Study Data Tabulation Model
SOC	System Organ Class
SVC	Slow Vital Capacity
TEAE	Treatment-Emergent Adverse Event

WHODrug	World Health Organization Drug Dictionary
---------	---

1. Introduction

The purpose of this statistical analysis plan (SAP) is to describe the planned analyses and reporting for protocol AT-1501-A201, Version 04 dated 08MAR2021.

This SAP is being written with due consideration of the recommendations outlined in the most recent International Conference on Harmonisation (ICH) E9 Guideline entitled Guidance for Industry: Statistical Principles for Clinical Trials and the most recent ICH E3 Guideline entitled Guidance for Industry: Structure and Content of Clinical Study Reports.

This SAP describes the data that will be analyzed and the subject characteristics, safety and tolerability, efficacy, biomarker, immunogenicity, and pharmacokinetic (PK) assessments that will be evaluated. This SAP provides details of the specific statistical methods that will be used. The statistical analysis methods presented in this document will supersede the statistical analysis methods described in the clinical protocol. If additional analyses are required to supplement the planned analyses described in this SAP, they may be completed and will be identified in the clinical study report.

2. Study Objectives

The primary objective of the study is to determine the safety and tolerability of intravenous (IV) administration of multiple doses of AT-1501 (planned 1.0, 2.0, 4.0, and 8.0 mg/kg).

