3.1 General Study Design

This is a Phase 2a, multi-center, open label, multiple dose study of AT-1501, a humanized monoclonal antibody antagonist to CD40LG. Approximately 54 adults with ALS will be enrolled into the study at up to 12 ALS treatment sites in the United States and one site in Canada.

Four ascending doses of AT-1501 (1.0 mg/kg, 2.0 mg/kg, 4.0 mg/kg, and 8.0 mg/kg) will be administered as a 1-hour IV infusion to sequentially enrolling cohorts. The 1.0 mg/kg and 2.0 mg/kg cohorts will consist of 9 participants each and the 4.0 mg/kg and 8.0 mg/kg cohorts will consist of 18 participants each. The participants in each cohort will receive 6 bi-weekly (every other week) infusions of AT-1501 over an 11-week period.

This study consists of a 4-week screening period, an 11-week dosing period in which participants are dosed once every other week, and a 4-week follow-up period. On Day 1, eligible participants will receive their first 1-hour IV infusion of AT-1501 and will be observed for at least 2 hours post infusion before being released. They will return on Weeks 3, 5, 7, 9, and 11 for subsequent infusions and will remain at the clinical site for at least 2 hours for observation and assessments before being released. Participants will be called weekly between dosing visits (Weeks 2, 4, 6, 8, 10, and 12) by a member of the research team to record AEs and changes in concomitant medications. Participants will be followed for an additional 4 weeks after their last dose to monitor for safety, with an end of study clinic visit occurring at Week 15.

Each participant will be monitored for safety throughout the study. Safety will be assessed by evaluation of AEs, changes in safety laboratory parameters, physical examination including vital signs, ECGs, and the C-SSRS. [REDACTED]

[REDACTED]

The Data Monitoring Committee (DMC) will meet following the administration of 6 doses to a minimum of 33% of participants in each cohort to review safety data and to make dose escalation recommendations to Anelixis. The meetings for Dosing Cohorts 1 and 2 will be held after 3 participants have received 6 doses, for a total of 18 doses. The meetings for Dosing Cohorts 3 and 4 will be held after 6 participants have received 6 doses, for a total of 36 doses. The Schedule of Visits and Assessments is provided in the Appendix. Full details of each assessment and other design considerations can be found in the study protocol.

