4.1 Method of Assigning Subjects to Treatment Groups

The potential participant who signed the informed consent form and met all the inclusion criteria and none of the exclusion criteria will be allowed to participate. Nine participants will be enrolled into each of the 1.0 mg/kg and 2.0 mg/kg cohorts and 18 participants will be enrolled into each of the 4.0 mg/kg and 8.0 mg/kg cohorts. Dose escalation decisions will be made by Anelixis with input from the DMC and Investigators. After the decision has been made to continue dosing a cohort, the next dose cohort will be allowed to start

once the last participant enrolled to the current cohort has received their first dose. The same process will be followed to move to the next dose cohort. The planned dose escalation scheme may be amended based on review of the emerging data. Additional cohorts may be added, and smaller cohort sizes may be implemented based on safety data and AT-1501 serum concentration results.

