4.2 Blinding and Unblinding

This study is an open label study, therefore blinding and unblinding procedures do not apply.

5. Sample Size and Power Considerations

Approximately 54 adults with ALS will be enrolled into the study. All participants will receive AT-1501. The sample size for this study is not based on formal statistical computation. The number of participants by dose group has been chosen in order to examine initial safety at lower doses [REDACTED]

[REDACTED] The sample size may increase in order to allow for replacement of subjects who are withdrawn or withdraw prior to receiving at least 4 infusions of AT-1501.

6. Data Preparation

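### SAP 13.1 plans no adverse-event table by dose number or study period and does not tabulate the during/after-infusion onset class, so AE trends over repeated doses can be seen only in listings

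*SAP*

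**What the plan says.** SAP section 2 sets the aim: to "determine the safety and tolerability of intravenous (IV) administration of multiple doses of AT-1501". SAP 3.1 fixes the exposure: "The participants in each cohort will receive 6 bi-weekly (every other week) infusions of AT-1501 over an 11-week period".

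SAP 13.1 counts as treatment-emergent anything that starts or worsens from the first dose onward. It plans an overall summary (number of TEAEs, and number and percentage of participants with at least one) and then tables by system organ class and preferred term: "Separate summaries will be provided for TEAEs using discrete summary statistics and presented by dose group and for all subjects by SOC and PT". Further tables are by preferred term alone and by maximum CTCAE grade. Repeats are collapsed in the SOC/PT tables: "If a subject reports the same PT multiple times within the same SOC, that PT will only be reported once within that SOC".

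The table list in SAP section 18 numbers the AE tables 14.3.1.1 to 14.3.1.6 without a gap. No title mentions dose number, visit, period or onset stage. The laboratory, vital-sign and ECG titles in the same list all say that they are by visit.

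Protocol 10.1.3 adds a data item: "The Investigator will classify the onset of each AE relative to the following stages of treatment", namely during or after the infusion. No readable AE table in the SAP uses it.

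**The concern.** The trial gives repeated infusions and asks whether they are safe. AE incidence is the first-named part of the primary endpoint, but the dimension of repetition is absent from every AE table. A risk concentrated at the first infusion, a steady risk and a risk that builds up can all produce the same printed percentage.

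Two other features add weight:

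- **The dose-limiting-toxicity window covers early dosing only.** Under Protocol 10.3 it closes when the sixth participant of a cohort receives the second dose. It is not designed to describe doses 3 to 6.
- **The denominator mixes exposures.** Protocol 6.5 replaces participants who leave before a fourth dose. Anyone with at least one dose stays in the Safety Analysis Set, so people who never received later doses still count in the percentages.

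At stake is whether the report can describe in figures how AE risk behaved over six infusions, or must leave readers to work it out from listings.

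**Working it through.** **Plan's own figures.** Cohorts (SAP 4.1): 9 + 9 + 18 + 18 = 54, as stated. Planned infusions: 54 × 6 = 324, that is 54 in each cohort of 9 and 108 in each cohort of 18. There is no power calculation to reproduce: "The sample size for this study is not based on formal statistical computation".

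**Assumptions.** The documents give no AE risk per dose, so every risk below is an assumption. The calculations take all six doses as received and risks as independent between doses. Dilution is treated separately.

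**1. Two opposite patterns, one table entry** (cohort of 18)

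- Constant 5% per dose: incidence = 1 − 0.95^6 = 26.5%, and 18 × 0.2649 = 4.8 participants.
- 0% at doses 1-3, then q at doses 4-6: 1 − (1 − q)^3 = 0.2649 gives 1 − q = 0.95² = 0.9025, so q = 9.75%. Incidence is again 26.5%, or 4.8 of 18.
- First events at doses 1-3 versus 4-6, constant: 18 × (1 − 0.95^3) = 2.6 versus 18 × (0.2649 − 0.1426) = 2.2. Late pattern: 0 versus 4.8.
- The planned count of TEAEs does not separate them either: 18 × 6 × 0.05 = 5.4 expected events against 18 × 3 × 0.0975 = 5.3.

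**2. A less extreme pattern, over a range.** Let risk rise in proportion to dose number (sixfold from dose 1 to dose 6), scaled so that whole-study incidence equals that of a constant risk p.

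| p | Rising risk, dose 1 to 6 | Incidence (both) | Expected events in 18, constant / rising | Share of first events at doses 4-6, constant / rising |
|---|---|---|---|---|
| 2% | 0.6% to 3.4% | 11.4% | 2.2 / 2.2 | 49% / 70% |
| 5% | 1.4% to 8.5% | 26.5% | 5.4 / 5.4 | 46% / 69% |
| 10% | 2.8% to 16.9% | 46.9% | 10.8 / 10.7 | 42% / 66% |
| 15% | 4.2% to 25.2% | 62.3% | 16.2 / 15.9 | 38% / 63% |

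Incidence is identical and event counts nearly so. The share at later doses differs (38-49% versus 63-70%), but no planned table shows it.

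**3. Dilution by replaced participants.** Assume 10% per dose, so 18 completers have incidence 1 − 0.9^6 = 46.9%. Add four people who stopped after one dose (10% each): (18 × 0.4686 + 4 × 0.10) / 22 = 40.2%. With two such people it is 43.2%. If they stopped after three doses, it is 44.9% for two and 43.3% for four. The per-dose risk is the same throughout.

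**4. What a table by dose could support.** With no events at one dose number, the two-sided 95% upper limit is 1 − 0.025^(1/n): 33.6% for n = 9 and 18.5% for n = 18. In simulations of 20,000 trials, an exact McNemar test of doses 1-3 against 4-6 under the sixfold rise had power of about 4% (p = 5%) to 15% (p = 10%) in one cohort of 18, and 30% to 60% with all 54 pooled.

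**5. Interval length.** Doses are nominally 14 days apart. From dose 6 (Day 71) to the final visit (Day 101) is 30 days. A constant 5% per 14 days becomes 1 − 0.95^(30/14) = 10.4% over 30 days. A table that took everything after dose 6 as one interval would show a false doubling at the end.

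**The case against.** A reader might infer that the trial cannot detect accumulating toxicity at all. The documents do not support that. SAP 13.2 to 13.4 summarise laboratory data, vital signs and ECG by visit with change from baseline. Box plots are planned for laboratory data, and within-visit change from pre-dose for vital signs. Platelets and coagulation, which the protocol synopsis singles out, are therefore followed across doses. The gap is confined to AEs.

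Nor is AE information by dose lost. SAP 8.4 has all study data listed unless otherwise specified, and listings of AEs and of dosing are planned. With about 54 participants, timing should be traceable case by case. The overall summary gives the number of TEAEs, so recurrence is not wholly removed. This stands, but listings supply no denominators or rates, and the SAP does not say that they will show onset relative to dose.

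It is also tempting to say that only repetition is new, because Phase 1 covered these dose levels. Protocol 3.4 shows that just three people with ALS received the drug, all at 1.0 mg/kg. The three higher levels are new in ALS at any dose number, so whole-study incidence by dose group is informative in its own right.

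Tabulating onset stage would not reveal accumulation, since it carries no dose number. It bears on infusion-time events, a separate question.

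Finally, cells would be small and there is no control arm in a progressive disease. Protocol 11.3.4 lists no AE summary by dose number, and SAP section 1 permits supplementary analyses. These points limit what the table can prove. They are weak reasons to leave it out of a trial that is descriptive throughout. Redaction is an unlikely explanation for the gap, because the AE table numbers are unbroken.

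**Conclusion.** The point holds for adverse events only. No planned table shows TEAEs by dose number or study period, and the onset class that the protocol collects is not tabulated. Whole-study incidence, even with the TEAE count, cannot distinguish constant from rising AE risk. Under the assumed risks, patterns with identical incidence differ in the share of first events at doses 4-6 by about 21 to 25 percentage points, and in the more extreme example the split is 2.6/2.2 against 0/4.8 in a cohort of 18. Early leavers kept in the denominator can lower incidence, by 6.7 points in the largest example (46.9% to 40.2%).

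These sizes rest on assumed risks and on independence between doses; they show what the tables would hide, not what will happen. The planned tables are not wrong, and by-visit laboratory, vital-sign and ECG data do address repeated exposure. This is a worthwhile, inexpensive addition, not a defect that invalidates the primary analysis.

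**What to change.** Add one descriptive table to SAP 13.1:

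- Participants with at least one TEAE (any; drug-related; Grade 2 or higher), by dose group and for all subjects, in equal 14-day windows after each dose k.
- Denominator: participants who received dose k. Recurrences are counted again in each window.
- Events more than 14 days after the last dose received go in a separate follow-up row. Alternatively, give every row as a rate per person-time.
- State which dose an event belongs to when visits shift. With ±2 days on each visit, successive doses can be 10 to 18 days apart; the person-time form handles this directly.

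Show the during/after-infusion split as a separate short summary of infusion-time events, and do not present it as evidence on accumulation.

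The cost is programming only: onset dates, dosing dates and the onset class are already needed or collected. The downside is sparse cells in all cohorts, not just the cohorts of 9. With no control arm, a late rise could reflect ALS progression. The SAP should therefore label the table descriptive and attach no test to it.

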13.2 Clinical Laboratory Data

Clinical laboratory data including chemistry, hematology, coagulation, serology, and urinalysis are collected at Screening, pre-dose on each dosing day, and at the end of study. Continuous parameters of chemistry, hematology, coagulation, and urinalysis will be summarized using continuous descriptive statistics at each scheduled visit (including a summary of baseline values) by dose group. Change from baseline to each post-baseline visit will be summarized. Serology lab data will only be presented in a listing. Box plots of laboratory data will be presented by dose group and visit.

Subject listings of all clinical laboratory results will be provided. In addition, separate subject listings of clinical laboratory abnormal results will be provided. Laboratory tests needing to be repeated for eligibility or safety that can not be sent to the central lab may be collected at the local laboratory and will be presented in a separate listing.

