The Data Monitoring Committee (DMC) will meet following the administration of 6 doses to a minimum of 33% of participants, in each cohort, (3 participants in cohorts 1 and 2 will have received 6 doses for a total of 18 doses, and 6 participants in cohorts 3 and 4 will have received 6 doses for a total of 36 doses) to review safety data and to make dose escalation recommendations to Anelixis.

**Target Population:** Adults with ALS who meet the inclusion/exclusion criteria.

[figure not shown]

**Safety:** Each participant will be monitored for safety throughout the study. Safety will be assessed by evaluation of AEs, changes in safety laboratory parameters (with special attention to platelet and coagulation values), physical examination including vital signs, ECGs and the C-SSRS.

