#### **10.1.1 Reporting of Adverse Events**

During the study, the Investigator or clinical site personnel will be responsible for querying and recording adverse events and serious adverse events. Events may be spontaneously reported by the participant, discovered during general questioning by the Investigator, or detected through physical examination, laboratory test or other means. Serious adverse events will be collected from the time of informed consent; all adverse events will be collected from the first administration of investigational product until completion of the final visit and will be evaluated by the Investigator/designee for duration, severity, seriousness, and relationship to investigational product, as outlined below. In addition, the actions taken for the AE will also be documented on the eCRF. Full laboratory data are to be collected in this study, and toxicity trends will be analyzed utilizing objective toxicity criteria.

A baseline recording of any symptoms of illness will be performed before administration of the investigational product. Only symptoms that increase in severity or frequency after investigational product administration or new symptoms of illness will be recorded as AEs. If the event reflects worsening symptoms, then this should be captured in the event term. Untoward medical events which occur after signature of the informed consent but before investigational product administration will be recorded as medical history.

For AEs occurring at the site of infusion the phrase “injection-site” or similar should be included in the event term (e.g. treatment-site erythema). AEs will be evaluated using the Common Terminology Criteria for Adverse Events (CTCAE Version 4.03). All AEs will receive a CTCAE categorization from the Investigator. AEs will also be categorized according to relatedness to the investigational product (see Section 0).

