### 10.3 Stopping Rules and Dose Limiting Toxicity (DLT)

The DLT observation period to determine the safety of a dose is defined as starting with administration of the first dose of AT-1501 to the first participant in a cohort through the administration of the second dose of AT-1501 in the 6th participant in that cohort. This will repeat for each dose level.

Any of the below outlined events occurring during the DLT observation period and considered to be **at least possibly related** to AT-1501 will qualify as a DLT.

A DLT is further defined as:

1. An event which meets the laboratory criteria for potential Drug Induced Liver Injury (DILI) or “Hy’s Law” defined as:
  - An elevated alanine transaminase (ALT) or aspartate transaminase (AST) lab value that is greater than or equal to three time (3x) the upper limit of normal (ULN) **WITH**
  - An elevated total bilirubin lab value that is greater than or equal to two times (2x) ULN without findings of cholestasis, **AND**
  - At the same time, an alkaline phosphatase (ALP) lab value that is less than 2x ULN
2. Any study drug related Grade 3 or greater toxicity with the exception of a Grade 3 or greater laboratory abnormality that is considered clinically insignificant and does not meet the criteria of an adverse event.
3. Any study drug related serious adverse event, regardless of severity.
4. A second occurrence of a similar Grade 2 or greater study drug related event within a cohort. That is, if two or more participants in a cohort experience a similar drug related AE greater than or equal to Grade 2 toxicity, a DLT has been met.

If any DLT criteria are met, further enrollment will be paused and the appropriate DLT data will be reviewed by Anelixis to determine an immediate course of action to be taken. If there are two or more occurrences of a DLT, the study may be temporarily halted until a more thorough safety review is undertaken.

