13.5 Columbia Suicide Severity Rating Scale

The C-SSRS will be administered at Screening, pre-dose on each dosing day, and at the end of study. The C-SSRS includes Yes/No questions and prompts for suicidal ideation and suicidal behavior.

A subject listing of the C-SSRS results will be provided.

15. Interim Analyses

No interim analysis is planned for this study.

16. Changes from Protocol-Stated Analyses

[figure not shown]
17. Revision History

Documentation of revision to the SAP will commence after approval of the final version 1.0.

18. Tables

Tables that will be included in the topline delivery are shown in italics, boldface font.

[figure not shown]
Table Number	Title	Population
Table 14.1.1	Subject Disposition	
Table 14.1.2	Subject Demographics and Baseline Characteristics	Safety Analysis Set
Table 14.1.3	Medical History	Safety Analysis Set
Table 14.1.4	Concomitant Medications	Safety Analysis Set
Table 14.1.5	Summary of Study Drug Dosing	Safety Analysis Set

Table 14.3.1.1	Summary of Treatment-Emergent Adverse Events	Safety Analysis Set
Table 14.3.1.2	Treatment-Emergent Adverse Events by System Organ Class and Preferred Term	Safety Analysis Set
Table 14.3.1.3	Drug-Related Treatment-Emergent Adverse Events by System Organ Class and Preferred Term	Safety Analysis Set
Table 14.3.1.4	Serious Adverse Events (SAEs) by System Organ Class and Preferred Term	Safety Analysis Set
Table 14.3.1.5	Treatment-Emergent Adverse Events by Preferred Term	Safety Analysis Set
Table 14.3.1.6	Treatment-Emergent Adverse Events by System Organ Class, Preferred Term, and Maximum CTCAE Grade	Safety Analysis Set
Table 14.3.2.1	Clinical Laboratory - Chemistry by Visit	Safety Analysis Set
Table 14.3.2.2	Clinical Laboratory - Hematology and Coagulation by Visit	Safety Analysis Set
Table 14.3.2.3	Clinical Laboratory - Urinalysis by Visit	Safety Analysis Set
Table 14.3.3	Vital Signs by Visit	Safety Analysis Set
Table 14.3.4	Electrocardiogram by Visit	Safety Analysis Set

19. Listings

Listing Number	Title
Listing 16.2.1	Subject Disposition
Listing 16.2.2	Inclusion/Exclusion Criteria for Screen Failed Subjects
Listing 16.2.3	Protocol Deviations
Listing 16.2.4.1	Demographics
Listing 16.2.4.2	Pregnancy Test for Female Subjects with Childbearing Potential
Listing 16.2.4.3	ALS Diagnosis
Listing 16.2.4.4	Medical History

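### Outside adverse event records, no visible SAP table counts participants by dose with graded laboratory values, the joint liver laboratory thresholds, or suicidal ideation or behaviour

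*SAP*

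**What the plan says.** Protocol 5.2.1 and SAP 2.2 name laboratory parameters and the C-SSRS as components of the primary safety endpoint. The protocol synopsis, under Safety, refers to "changes in safety laboratory parameters (with special attention to platelet and coagulation values". Protocol 10.1.1 adds: "Full laboratory data are to be collected in this study, and toxicity trends will be analyzed utilizing objective toxicity criteria".

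SAP 13.2 then sets the laboratory analysis: "Continuous parameters of chemistry, hematology, coagulation, and urinalysis will be summarized using continuous descriptive statistics at each scheduled visit". It also provides change from baseline by visit, box plots by visit, full listings and separate listings of abnormal results. Repeat tests that cannot go to the central laboratory "may be collected at the local laboratory and will be presented in a separate listing". The table list in SAP 18 agrees: Table 14.3.2.1 is titled "Clinical Laboratory - Chemistry by Visit", and Tables 14.3.2.2 and 14.3.2.3 are by visit as well.

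For the C-SSRS, SAP 13.5 describes Yes/No items and provides one output, a subject listing (Listing 16.2.8.6).

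For adverse events, SAP 13.1 does count people by dose: within SOC and PT, "the subject will be counted once under the maximum grade".

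**The concern.** In cohorts of 9 or 18, the natural safety result is how many participants at each dose crossed a toxicity threshold at any time on study. By-visit means, medians, minima and maxima do not give that number. They describe each test at each visit and do not follow a participant across visits or across tests. For findings not recorded as adverse events, a reader of the study report would have to assemble the number from listings. What is at stake is how clearly two primary-endpoint components are reported by dose; the data themselves are not at risk.

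**Working it through.** The plan gives no figure to reproduce here, and the sample size has no formal basis (protocol 11.1, SAP 5). The check is therefore mainly a comparison of text.

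**1. Inputs.** Cohorts: 9 + 9 + 18 + 18 = 54 (SAP 3.1). Scheduled post-baseline laboratory visits: Weeks 3, 5, 7, 9 and 11, plus Week 15, so 5 + 1 = 6 (protocol Appendix A).

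**2. Where each kind of finding is reported in the visible SAP.**

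| Finding | Visible output | Participants counted by dose? |
|---|---|---|
| Laboratory abnormality recorded as an AE | Tables 14.3.1.1 to 14.3.1.6 | Yes, including by PT and maximum grade |
| Graded value, not an AE, scheduled visit | Tables 14.3.2.1 to 14.3.2.3, box plots, listings | No; an extreme can show as a minimum or maximum |
| Graded value, not an AE, post-baseline unscheduled draw or local repeat | Listings | No |
| ALT/AST, bilirubin and ALP thresholds met together, not an AE | Separate summary per test, listings | No |
| Positive C-SSRS answer, not an AE | Listing 16.2.8.6 | No |

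**3. Do the AE tables close the gap?** Not fully. The second DLT criterion in protocol 10.3 makes an exception for "a Grade 3 or greater laboratory abnormality that is considered clinically insignificant and does not meet the criteria of an adverse event". The protocol therefore expects that some high-grade values will have no AE record, and these appear in no graded count.

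**4. Can the joint liver criterion be read from the separate summaries?** No. Protocol 10.3 combines ALT or AST at or above 3x ULN with total bilirubin at or above 2x ULN without cholestasis findings, and adds "At the same time, an alkaline phosphatase (ALP) lab value that is less than 2x ULN". Suppose that at one visit *a* of *n* participants exceed the ALT/AST limit and *b* exceed the bilirubin limit. The number exceeding both lies anywhere from max(0, a + b − n) to min(a, b). With a = b = 1 and n = 9 or 18, that is 0 or 1. The by-visit statistics do not supply *a* and *b* either. The DLT definition does not fill this gap in reporting: it also needs at least possible relatedness and a window that closes at the sixth participant's second dose, and the visible SAP has no DLT table.

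**5. Unscheduled values.** SAP 8.3 lets baseline come from an unscheduled assessment, so those values do enter the by-visit tables as baseline. The part that falls outside the tables, on a plain reading of SAP 13.2, is post-baseline unscheduled results.

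**6. How firm are the protocol statements?** Protocol 10.1.1 says the toxicity trends will be analysed, but it prescribes no table. Protocol 11.3.4 lists C-SSRS change from baseline among analyses that may be included. SAP 1 says that its methods supersede the protocol's.

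**7. What a count could say.** For zero affected participants, the exact two-sided 95% upper limit is 1 − 0.025^(1/n). This is 33.6% for n = 9 and 18.5% for n = 18. The added tables would describe the cohorts and could not rule out uncommon toxicity.

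The documents offer no basis for estimating how many participants would go uncounted.

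**The case against.** The strongest reply is that nothing is hidden. SAP 8.4 sorts listings by dose group and subject, abnormal results have their own listings, and counting 9 or 18 people by hand is easy. Minima, maxima and box plots expose extremes at scheduled visits. The endpoint is worded as changes in laboratory parameters, and SAP 13.2 delivers change from baseline. A clinically important abnormality would normally become an AE and be counted, while the exception in protocol 10.3 covers only values judged clinically insignificant. The DMC reviews all available safety and laboratory data, including platelets and coagulation (protocol 5.4). Few positive C-SSRS answers are likely: entry excludes active ideation with a plan, and no suicidal ideation was expressed in Phase 1.

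Most of this stands, and it limits the weight of the point. It does not remove it. SAP 13 says safety will be summarised by dose group, SAP 8.4 makes counts and percentages the convention for discrete variables, and a listing does neither. A zero by dose is also a reportable result.

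Hidden text is a fair reservation. SAP numbering passes from 13 to 15, and the content of section 16 is not shown. Table 14.3.2.3 is followed directly by 14.3.3, but a removed fourth laboratory table would leave no numbering gap. The laboratory part therefore rests mainly on the wording of SAP 13.2. A C-SSRS table could sit after Table 14.3.4, where the visible list ends.

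A reader might infer that the SAP breaks a protocol commitment. The documents do not support that: protocol 10.1.1 names no output and protocol 11.3.4 is permissive.

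**Conclusion.** The point holds as a modest reporting gap. In the visible SAP, outside AE records, no table counts participants by dose with graded laboratory values, with the joint liver laboratory thresholds, or with suicidal ideation or behaviour. Confidence is reasonable for the laboratory part and lower for the C-SSRS part. Both rest on the assumption that no hidden SAP text supplies these tables.

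Two stronger readings should be resisted. One is that laboratory toxicity, or a liver signal, could go unnoticed. All results are listed, the DMC sees the data, and a qualifying related event within the DLT window pauses enrolment for sponsor review. The other is that all unscheduled values are dropped; only post-baseline ones fall outside the by-visit tables. The change should be made because it is cheap and concerns primary-endpoint components. No analysis conclusion has been shown to be wrong.

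**What to change.** **SAP 13.2.** Add, by dose group, shift tables from baseline to each participant's worst post-baseline CTCAE v4.03 grade, using low/normal/high where no grade exists. Cover chemistry, platelets and coagulation. Include post-baseline unscheduled values, and include local repeats only where the local reference range is recorded; the documents do not say whether it is.

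Also add n (%) by dose group meeting the ALT/AST, bilirubin and ALP laboratory thresholds of protocol 10.3 at the same post-baseline visit. Label this table a laboratory screen and not a DLT, because relatedness, the DLT window and cholestasis findings are not applied.

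**SAP 13.5.** Unless hidden text already provides it, add n (%) by dose group with any suicidal ideation or behaviour at baseline and at any post-baseline visit.

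**Cost.** About four descriptive tables: chemistry shift, platelet and coagulation shift, liver laboratory screen, and C-SSRS (1 + 1 + 1 + 1 = 4), plus the SAP wording. No new assessment is needed, and the endpoint does not change. If such tables already exist in text that is not public, confirming that closes the point.
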